4.7.5 Use of Oral Bridging

When a participant plans for a missed injection, the participants may elect for oral bridging. Dosing of oral bridging in the event of missed doses will be in accordance with the most recent CABENUVA USPI.

A single occurrence of oral bridging will be defined as the period between two adjacent CABENUVA injections. If the participant is on oral bridging at the end of the study period, then the last occurrence of oral bridging is counted as between the last CABENUVA injection and the end of the study period. The duration of each oral bridging instance will be derived as the duration from start to end date of the use of oral HIV medication between two adjacent CABENUVA injections.

The number of occurrences and duration of each occurrence of oral bridging will be summarized in a table using the Safety Set.

Participants who have used oral bridging at least once will be summarized. This includes both the participants on a monthly injection schedule and an every-2-month injection schedule.

Frequency of the oral bridging occurrences will be summarized in a table and a histogram. This includes both the participants on a monthly injection schedule and an every-2-month injection schedule, while the max frequency for the former is eight and for the latter is four.

The missed injection rate at each visit for participants on oral bridging (proportion of participants who missed injection at scheduled visit N+1 while on oral bridging after visit N) will be summarized. Missed injection rate will be defined as one minus the adherence rate.

4.7.6 Impact of COVID-19 Pandemic

Incidence, severity, and outcome of COVID-19 diagnoses, changes to prescribing related to COVID-19, visit impact (e.g., missed visits, altered visit type), and study impact (e.g., need for remote visits, discontinuation of study treatment, discontinuation of study) will be listed.

4.7.7 Changes from Planned Analysis

As the data are analyzed, some deviation from expectations may occur. In instances where these deviations would make the proposed analyses inappropriate, modifications to the SAP—along with justifications for these changes—will be made and noted in the final report.

5 Limitations on Research Methods

This is a single-arm, real-world study for gathering information on the feasibility and acceptability of utilizing an IC/ASA to administer CABENUVA in the US. As such, participants may not necessarily be representative of the general population and certain demographics may be over- or under-represented.

6 References

- 1. World Health Organization. *Global Surveillance for human infection with novel coronavirus (2019-nCoV): interim guidance, 31 January 2020*. 2020. 2020. https://apps.who.int/iris/handle/10665/330857

7 Appendices

7.1 Schedule of Activities (SoA)

Procedure ¹	Baseline/ Month 1 ²		Treatment Period (Months)							
		2	3	4	5	6	7	8		

- The timing and number of planned study assessments may be altered during the study based on newly available data.
- 2. The following sequence of events must be followed for participants at the Baseline/Month 1 visit: 1) informed consent form (ICF) Consent 2) confirm inclusion and exclusion criteria 3) complete questionnaires and assessments, 4) receive first study-related intramuscular (IM) injections at the IC/ASA. Baseline is defined as the Month 1 visit.
- 3. E.D. = early discontinuation/withdrawal: This visit should only be conducted if the participant discontinues from the study, and the discontinuation/withdrawal reason should be recorded.

NOTE: Carefully follow the Instructions for Use when preparing and administering CABENUVA IM to avoid accidental intravenous administration

Clinical and Other Assessments

Clinical and Other Assessments										
Informed Consent	X									Written informed consent must be obtained from each potentially eligible participant by IC/ASA personnel prior to the initiation of any Baseline procedures as outlined in this protocol.
Inclusion and Exclusion Criteria	Х									Inclusion/exclusion criteria will be fully assessed at the Baseline/Month 1 Visit.
Demography	Χ									
Pregnancy Status	Х	Х	X	X	Х	Х	X	X	Х	Ask POCBP at each visit if they are pregnant and ask for the date of their LMP. See Protocol Section 10.3.11 for additional information. For participants on every-2-month injections, pregnancy status should be confirmed only at IC/ASA visits.
Height and Weight	Х	Х	Х	Х	Х	Х	Х	Х	X	Height will only be collected at Baseline. BMI will be calculated within the eCRF. If possible, the same scale should be used consistently throughout the study and participants should be asked to remove any excess clothing (i.e., coats and shoes).

										For participants on every-2-month injections, weight will be collected only at IC/ASA visits.
Vital Signs: Blood Pressure, Heart Rate	X				ording to the din the par		Vital signs are to be measured after resting in a semi-supine position for at least 5 minutes. For participants on every-2-month injections, vital signs will be collected only at IC/ASA visits.			
Laboratory								Х		The Baseline/Month 1 labs should be collected prior to the first study injection (at the Baseline/Month 1 visit). See Section 10.1 for additional information
Assessments (HIV1- RNA, Liver Chemistries, Other Labs Per POT)	Х	the HIV	care provid	der. All lab source do	be obtained reports must cumentation otherwise r	Х	The HIV care provider is responsible for monitoring and any follow-up of elevated HIV-1 RNA and liver chemistries in their PLWHIV and tet the IC/ASA know if there are any changes to the monthly or every-2-month injections. The F-care provider can request that the IC/ASA draw labs at any time or they can perform local labs a required.			
Study Treatment: All inj	ections will be	e administer	ed accordin	g to the CA	ABENUVA US	SPI				
CABENUVA IM Injection	s initiated at		The final oral doses of CAB + RPV, or other ART, should be taken on the same day when injections with CABENUVA are started. Questionnaires and procedures should be conducted prior to the injections.							
Monthly Dosing (Post Oral Lead-In)	X	Х	Х	Х	X	Х	Х	Х		IM dosing is expected to occur on the same date of the month as determined by Dose 1 - Treatment Target Date. Dosing window is ±7 days.
Every-2-month Dosing	Х	Х		Χ		Х		Х		Dosing window for every-2-months is \pm 7 days.
CABENUVA IM Continua subsequent injections a	•		already red	ceiving CAB	BENUVA inje	ections, and	who are to	get their		Questionnaires and interviews should be conducted prior to the injections.

Note: To avoid having participants whose last injections are at Month 7 return to the IC/ASA at Month 8, the end of study assessments (Month 8) will be completed at Month 7. Questionnaires and potential interviews will be completed at Month 8.										
Monthly Dosing	Х	X	X	Х	Х	Х	X	Х		The first study-related CABENUVA injections at the IC/ASA should be started within 1 month (±7 days) after the last injections. For participants switching from an every-2-month continuation injection schedule to a monthly continuation dosing schedule, follow the dosing instructions in the most recent USPI for CABENUVA.
Every-2-month Dosing (Participants Already Receiving Every-2-month Dosing)	X		X		Х		X			Dosing window for every-2-month dosing is ±7 days. For participants switching from a monthly continuation injection schedule to an every-2-month continuation injection dosing schedule follow the dosing instructions in the most recent USPI for CABENUVA.
Concomitant Medication Review	Х	?====	======	======	======	Х	The IC/ASA will note all new concomitant medications and send to the HIV care provider. Contraindicated medications and concomitant medications with a potential for a DDI per CABENUNVA USPI will be recorded.			
Adverse Event (AE) Review	Х	?====	======	======	======	Х	See Protocol Section 10 for more information on the DAIDS grading scale, Protocol Section 10.3.7 for guidelines on assessment of causality, and Protocol Section 10.3.10 for AE reporting requirements. Refer to the Protocol Annex 3 for definitions of AEs.			
Serious AEs (SAEs)	X	?====				Х	See Protocol Section 10 for more information on the DAIDS grading scale, Protocol Section 10.3.7 for guidelines on assessment of causality, and Protocol Section 10.3.10 for SAE reporting requirements. Refer to the Protocol Annex 3 for definitions of SAEs			

Abbreviations: AE = adverse event; ART = antiretroviral therapy; ASA = alternative site of administration; DDI = drug-drug interaction; E.D. = early discontinuation/withdrawal; HIV = human immunodeficiency virus; IC = infusion center; ICF = informed consent form; IM = intramuscular; LMP = last menstrual period; POCBP = person of child-bearing potential; PLWHIV = People living with human immunodeficiency virus; POT = plan of treatment; RNA = ribonucleic acid; SAE = serious adverse event; USPI = United States prescribing information

7.2 Protocol Deviations Rules Document

[At DBL, will be placed in this appendix.]

7.3 Tables and Listings

EVA 30466- Clinical Table Shells_Final_V Listing Shells_Final_

7.3.1 Tables

Table 14.1.1 Summary of Participant Disposition (Enrolled Set)

Table 14.1.2 Summary of Important Protocol Deviations (Enrolled Set)

Table 14.1.3 Summary of Demographics and Baseline Characteristics (Enrolled Set)

Table 14.1.4 Summary of Medical History (Enrolled Set)

Table 14.1.5 Summary of Prior Medications (Excluding ARTs) (Enrolled Set)

Table 14.1.6 Summary of Prior Antiretroviral Therapies (Enrolled Set)

Table 14.1.7 Summary of Concomitant Medications (Excluding ARTs) (Safety Set)

Table 14.1.8 Summary of Concomitant Antiretroviral Therapies (Safety Set)

Table 14.1.9 Summary of Study Treatment Exposure Prior to Enrollment (Safety Set)

Table 14.2.1 Summary of HIV-1 RNA Over Time (Safety Set)

Table 14.2.2 Summary of HIV-1 RNA Changes from Baseline (Safety Set)

Table 14.3.1 Summary of Study Treatment Exposure (Safety Set)

Table 14.3.2 Summary of CAB + RPV Exposure (Safety Set)

Table 14.3.3 Summary of Missed CABENUVA Injections (Safety Set)

Table 14.3.4 Summary of Oral Bridging (Safety Set)

Table 14.3.5 Summary of Baseline Adverse Events (Safety Set)

Table 14.3.5.1 Summary of Baseline Adverse Events by SOC and PT (Safety Set)

Table 14.3.6 Summary of Adverse Events (Safety Set)

Table 14.3.6.1 Summary of Adverse Events by SOC and PT (Safety Set)

Table 14.3.7 Summary of Injection Site Reaction Adverse Events (Safety Set)

Table 14.3.8 Summary of Treatment-Related Adverse Events (Safety Set)

Table 14.3.8.1 Summary of Treatment-Related Adverse Events by SOC and PT (Safety Set)

Table 14.3.9 Summary of Adverse Events Leading to Treatment Discontinuation or Study Withdrawal (Safety Set)

Table 14.3.9.1 Summary of Adverse Events Leading to Treatment Discontinuation or Study Withdrawal by SOC and PT (Safety Set)

Table 14.3.10 Summary of Serious Adverse Events (Safety Set)

Table 14.3.10.1 Summary of Serious Adverse Events by SOC and PT (Safety Set)

Table 14.3.11 Summary of Cardiovascular Event Status (Safety Set)

Table 14.3.12 Summary of Liver Monitoring / Stopping Events (Safety Set)

Table 14.3.13 Summary of Hepatobiliary Laboratory Abnormalities (Safety Set)

Table 14.3.14 Summary of Clinically Significant or Abnormal Lab Values (Safety Set)

Table 14.3.14.x Summary of Clinically Significant or Abnormal Lab Values by Lab Parameter (Safety Set)

Table 14.3.15 Summary of CD4 Results and Changes from Baseline (Safety Set)

Table 14.3.16 Summary of Vital Sign Changes from Baseline (Safety Set)

Table 14.3.17 Summary COVID-19 Adverse Events (Safety Set)

Table 14.3.17.1 Summary COVID-19 Adverse Events by SOC and PT (Safety Set)

Table 14.3.18 Summary of COVID-19 Study Impacts

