#### Type of Participant and Disease Characteristics

- 2 HIV-1 infected and have been prescribed CABNEUVA per the USPI. Participants can be enrolled:
  - If they have been taking oral VOCABRIA + EDURANT or other ART for approximately 1 month (at least 28 days) prior to Baseline/Month 1, or
  - Already taking CABENUVA prior to Baseline/Month 1 and the last injections
    were within a 1 month ± 7-day window or for every 2-month injections, the
    timing will vary they are receiving the initiation injections (1 month ± 7-day) or
    the continuation injections (2 months ± 7 days) per the USPI, or
  - Prescribed direct to inject and receive their 1st injection without an oral lead in at the Infusion Center on the last day of any other antiretroviral therapy.

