# 4.3. Study Groups and Duration

This study will include the following groups: An Expert Panel, HIV care providers, virologically suppressed PLWHIV seeking to start or continue CABENUVA for treatment for HIV-1, and the IC/ASA staff. A CABENUVA POT will be agreed between the HIV care provider and the IC/ASA prior to study participants receiving their first study related injections at the IC/ASA.

Assessments can be found in Annex 1: Schedule of Activities and in the POT.

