4.1.1.2 Continuous Data

The following summary statistics will be reported for continuous data:

- n: number of distinct participants with non-missing observations
- Mean (standard deviation [SD]): arithmetic mean, SD)
- Median
- Interquartile range (IQR; i.e., 25th percentile [Q1] 75th percentile [Q3])
- Min, Max: minimum, maximum

If n=1, SD will be displayed as "N/A" (i.e., not applicable) and CIs as "NE" (i.e., not estimable). SD will be rounded and displayed with two more decimal places than the reported value. All mean, median, Q1, and Q3 values will be rounded and displayed to one more decimal place than the reported value. CI values will be rounded and displayed to one more decimal place than the parameter estimate. Min and max values will be displayed consistent with the number of decimal places in the reported value.

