4.1.2 Baseline Definition

Baseline will be defined as the date when a participant signs the ICF and completes the Baseline/Month 1 protocol procedures prior to receiving the first study-related CABENUVA injections at the IC/ASA.

All additional study visits will be anchored from each participant's Baseline/Month 1 visit, and will therefore reflect the months on study, regardless of what injection schedule they are on and regardless of whether they have missed any injections and received oral bridging.

Change from baseline will be calculated as the difference between the baseline and post-baseline values, which have the same number of decimal places. Percent change from baseline will be calculated by dividing change from baseline by non-zero baseline value, rounded and reported to one decimal place.

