4.1.3 Missing Data Handling

For the purposes of classifying medications/therapies as prior or concomitant, or for AEs as pretreatment, on-treatment, or post-treatment, incomplete dates may be imputed.

Details for handing missing AE relatedness, severity, seriousness, etc. are discussed in Section 4.7.1.1.

No other missing data will be imputed.

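### The visible SAP text gives HIV-1 RNA change from baseline only a raw-difference and percent rule, with nothing for results below an assay limit

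*SAP*

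**What the plan says.** The table list in section 7.3.1 of the clinical SAP includes "Table 14.2.2 Summary of HIV-1 RNA Changes from Baseline (Safety Set"). It is one of two tables in the 14.2 series; the other summarises HIV-1 RNA over time.

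The general rule is in section 4.1.2: "Change from baseline will be calculated as the difference between the baseline and post-baseline values". The next sentence adds: "Percent change from baseline will be calculated by dividing change from baseline by non-zero baseline value". The direction of subtraction is not stated. The percent rule sets aside zero baselines only. Section 4.1.1.2, which begins "The following summary statistics will be reported for continuous data", lists n, mean (SD), median, interquartile range, minimum and maximum. Section 4.1.3 allows imputation of incomplete dates, refers to a later section for missing adverse-event attributes, and then closes the list: "No other missing data will be imputed".

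Section 4.7.4 (Effectiveness) plans a per-visit summary of HIV-1 RNA and two proportions with exact intervals: suppression below 50 copies/mL, and confirmed failure on two consecutive values of 200 or more. It mentions no change analysis, log10 scale or treatment of below-limit results. Section 4.7.2 says that results come from different laboratories and that there is no central one.

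The protocol (4.3) describes the participants as "virologically suppressed PLWHIV seeking to start or continue CABENUVA for treatment for HIV-1". The inclusion criterion asks only that they be "HIV-1 infected and have been prescribed CABNEUVA per the USPI" and sets no HIV-1 RNA threshold.

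**The concern.** In a suppressed population many HIV-1 RNA results are likely to arrive as below some limit, or as not detected, rather than as a number. Such a result cannot be subtracted from another or used as a denominator. The limit may also vary within one person. Protocol 10.1 lets baseline blood be drawn off-site or taken from results that the provider shares, and Annex 1 lets later tests be done at the infusion center or locally by the provider. The harmonisation text in SAP 4.7.2 deals with reference values, not quantification limits.

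Without a stated rule, whoever programs the table must choose, with the data in hand, between leaving most changes blank and coding them at a limit. The second choice can show a mean rise when almost nobody changed, or a change that reflects only two assay limits. The table sits under effectiveness in a single-arm study, so a reader could take either for a finding.

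**Working it through.** The plan states no figure for this table: no assay limit, no share of results below it and no expected number of viraemic people. There is nothing to reproduce, and the inputs below are assumptions shown over ranges. From the documents come the maximum of 120 participants, the 4.1.2 rule, the 4.1.1.2 statistics and the cut-offs of 50 and 200 copies/mL.

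The two cases are alternatives. Which one applies depends on how a below-limit result is coded.

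**Case A: below-limit results left as reported.** Let q be the share below the limit at each visit. A change is computable only if both values are numbers. The share without a change is q if the same people are below the limit at both visits, and 1 - (1 - q)² if the visits are independent.

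| q (assumed) | Quantifiable baselines at N = 120: 120 × (1 - q) | No change computable: q to 1 - (1 - q)² |
|---|---|---|
| 50% | 60 | 50% to 75% |
| 80% | 24 | 80% to 96% |
| 90% | 12 | 90% to 99% |
| 95% | 6 | 95% to 99.75% |
| 98% | 2.4 | 98% to 99.96% |

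Half or more of the participants drop out of the change summary even at q = 50%. A person who goes from below the limit to a high value drops out too.

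**Case B: below-limit results coded at the limit.** Take N = 120, everyone coded 50 copies/mL at baseline, 119 unchanged and one person at v. The mean change is (v - 50)/120, the SD is (v - 50)/√120, and the mean log10 change is log10(v/50)/120.

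| v (assumed) | Mean, copies/mL | SD | Median (IQR) | Mean log10 |
|---|---|---|---|---|
| 1,000 | 950/120 = +7.9 | 87 | 0 (0 to 0) | 0.011 |
| 10,000 | 9,950/120 = +82.9 | 908 | 0 (0 to 0) | 0.019 |
| 100,000 | 99,950/120 = +832.9 | 9,124 | 0 (0 to 0) | 0.028 |

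Two people at 100,000 give 2 × 99,950/120 = +1,665.8. With N = 60, one person at the same three values gives +15.8, +165.8 and +1,665.8. If mean percent change were shown at N = 120, it would be the mean change divided by 50: +15.8%, +165.8% and +1,665.8%.

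**Differing limits, also under Case B.** With no viral change, coding 20 at baseline and 50 later gives +30 copies/mL, or 30/20 = +150%. The reverse order gives -30 copies/mL, or -30/50 = -60%.

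**The case against.** The strongest objection is that the table itself cannot be seen. Section 7.3 embeds the shells as files that did not survive extraction, and the tertiary endpoint text is blacked out or missing from the readable copy. The title would fit a shift table or a log10 table as well as a raw difference. This stands: one can say only that the visible text does not define the table, not that the plan lacks a rule.

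A reader might infer more than the documents support in four ways.

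- That nearly all values will be below the limit. No share is given, no entry criterion sets a threshold, and suppression means below 50 copies/mL, so a laboratory with a lower limit could report numbers under 50.
- That the table is both blank for most people and dominated by one or two. Cases A and B exclude each other.
- That percent change will be shown. Section 4.1.2 says how to compute it, not which tables carry it.
- That the whole summary is distorted. The planned median and interquartile range stay at 0 in Case B, and a listing gives every HIV-1 RNA result.

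The objection also notes that the objectives are tertiary, that the sample size was not powered for clinical outcomes, and that the two proportions in 4.7.4 do not use this table. That lowers the severity. It does not supply the missing rule.

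**Conclusion.** The point holds as a minor gap in the visible SAP text. The general change rule does not suit HIV-1 RNA in a population described as suppressed and tested at several laboratories. Read literally, it yields either no value for many participants or a mean, SD and percent change set by a few people and by assay limits. The sizes above rest on assumed shares, limits and viral loads. Two conclusions hold across the ranges tried: under Case A at least half of the participants have no change value once half of results are below the limit, and under Case B the mean moves while the median stays at 0.

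A reader might infer that the effectiveness results are unsound. The documents do not support that: suppression and confirmed failure are unaffected where local limits are at or below 50 copies/mL.

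**What to change.** In section 4.7.4, state that the raw and percent change of 4.1.2 do not apply to HIV-1 RNA. Define Table 14.2.2 as a shift table of baseline against each scheduled visit, with categories below 50, 50 to below 200, 200 or more copies/mL, and missing. Flag separately any result reported as below a limit that itself exceeds 50, because its category is unknown. Give log10 change, as post-baseline minus baseline, only where both values are quantifiable, and show how many participants that covers.

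Check the shells first. If they already contain such a rule, carry it into 4.7.4.

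The cost is a short addition to 4.7.4 and a revised shell, with no new data. The categories need no substitution where local limits are at or below 50 copies/mL.

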7.3.2 Listings

Listing 16.1.1 Participant Disposition (Enrolled Set)

Listing 16.1.2 Screen Failures (Enrolled Set)

Listing 16.1.3 CABENUVA Discontinuation (Safety Set)

Listing 16.1.4 Protocol Deviations (Enrolled Set)

Listing 16.1.5 Prohibited Medications (Enrolled Set)

Listing 16.1.6 Demographics and Baseline Characteristics (Enrolled Set)

Listing 16.1.7 Medical History (Enrolled Set)

Listing 16.1.8 Cardiovascular Risk Factors (Safety Set)

Listing 16.1.9 Prior Antiretroviral Therapy (Enrolled Set)

Listing 16.1.10 Current Antiretroviral Therapy (Safety Set)

Listing 16.1.11 Prior Concomitant Medications (Excluding ARTs) (Enrolled Set)

Listing 16.1.12 Current Concomitant Medications (Excluding ARTs) (Safety Set)

Listing 16.3.1 Study Treatment Initiation Method (Safety Set)

Listing 16.3.2 Study Treatment Administration (Safety Set)

Listing 16.3.3 Study Treatment Change in Regimen (Safety Set)

Listing 16.3.4 Missed CABENUVA Injections (Safety Set)

Listing 16.3.5 Use of Oral Bridging (Safety Set)

Listing 16.3.6 Baseline Adverse Events (Safety Set)

Listing 16.3.7 Adverse Events (Safety Set)

Listing 16.3.8 Injection Site Reaction Adverse Events (Safety Set)

Listing 16.3.9 Adverse Events Leading to Study Discontinuation (Safety Set)

Listing 16.3.10 Serious Adverse Events (Safety Set)

Listing 16.3.11 Liver Monitoring / Stopping Events (Safety Set)

Listing 16.3.12 Pregnancies Occurring During Study (Safety Set)

Listing 16.3.13 Pregnancy-Related Adverse Events (Safety set)

Listing 16.3.14 HIV-1 RNA Clinical Lab Results (Safety Set)

Listing 16.3.15 Liver Chemistry Clinical Lab Results (Safety Set)

Listing 16.3.16 Other Clinically Significant or Abnormal Value Clinical Lab Results (Safety Set)

Listing 16.3.17 Vital Signs and Anthropometrics (Safety Set)

Listing 16.3.18 12-Lead ECG Results (Safety Set)

A Phase 4, Open-label, Single-arm Study to Optimize Implementation of CABENUVA for the Treatment of HIV-1, for Administration in US Community-based Infusion Centers

Listing 16.3.19 COVID-19 Adverse Events (Safety set)

Listing 16.3.20 COVID-19 Study Impact (Safety Set)

Statistical Analysis Plan: Infusion Center or Alternate Site of Administration Staff

EVA-30466 | March 4th, 2024 | Version 4

Prepared F	or:	
PPD		, GSK
PPD	, PhD PPD	, Global Implementation Research, ViiV Healthcare
ViiV Healthcare		
Prepared B	y:	
PPD	, PhD	
PPD	PhD MPH	
[name]	
Project Cor	ntact:	
PPD		

Statistical Analysis Plan (SAP) Signature Page

SAP Title:

